8.4 HANDLING OF MISSING DATA

Unless specified otherwise, no imputation of missing data will be performed.

Adverse Event (AE) start dates will not be imputed. In case of an incomplete or missing start date, AEs will be classified as treatment-emergent unless sufficient information is available to conclude that the event started or worsened before the first study treatment (e.g., if only the year is available and it matches the year of the first study treatment date, the event will be considered treatment-emergent).

In order to distinguish prior and concomitant medications/procedures, the end date will be compared to the start date of the study medication/procedure. Incomplete end dates will not be imputed. Medications/procedures will be flagged as both prior and concomitant if there is uncertainty (e.g., missing end date, while month and year are equal to study treatment start and start date is before the date of study treatment start).

8.5 PATIENT DISPOSITION

Patient screening data (informed consent, screening failures, and their reasons, enrollment) will be tabulated for Screened set. Enrollment by country will be tabulated and listed. Numbers of patients in all the study populations will also be presented. Completion and reasons for premature discontinuation from treatment and study will be summarized for Safety and PK sets. Time on study (weeks) will also be summarized. It will be defined as the time between the first dose of the study drug and study completion/discontinuation.

^{**} This is for patients who complete 12 weeks of treatments. An End of Treatment/Early termination (EOT/ET) visit will be performed 4 weeks after the last dose of pegcetacoplan. For patients who complete 12 weeks of treatment, the EOT visit will be at Week 16, and there will be further follow-up visits at Weeks 20 and 24. For patients who complete 16 weeks of treatment, the EOT visit will be at Week 20, and there will be a further follow-up visit at Week 24.

Page 20 of 39

Patients who discontinued due to a coronavirus disease 19 (COVID-19)-related reason will have their reason for discontinuation classified and summarized as such.

8.6 PROTOCOL DEVIATIONS

Study-specific protocol deviations considering the operational aspect of the study conduct, including deviations as a result of the COVID-19 pandemic, will be classified as Minor or Major at database lock (DBL).

Major protocol deviations will be tabulated for the ITT and PK sets.

Major protocol deviations due to COVID-19 will be identified and summarized separately.

The monitoring of Quality Tolerance Limits was not implemented due to study sample size. Risk control measures that were used to protect data integrity and subject safety will be described in the clinical study report.

8.7 PATIENT CHARACTERISTICS

Patient characteristics will be summarized for ITT and PK sets.

8.7.1 Baseline and Demographic Characteristics

Demographics (age, age in categories, sex, race, ethnicity, child-bearing potential, and method of contraception) and baseline characteristics (weight, height) will be summarized.

Age categories: age is defined as 2 categories:

- Adults (18 to 64 years)
- From 65 to 84 years

Alcohol consumption and smoking habits (presence or absence of each habit and frequency) will be summarized.

8.7.2 MEDICAL HISTORY AND CURRENT MEDICAL CONDITIONS

Medical history (conditions that ended before the date of enrollment) and current medical conditions (those that started before and were ongoing at the date of enrollment) will be coded using the Medical Dictionary for Regulatory Activities (MedDRA) version current at the time of DBL and tabulated by System Organ Class (SOC) and Preferred Term (PT).

Baseline TA-TMA data will be summarized using the following variables:

- The platelet value at the diagnosis (10^9/L),
- The highest platelet value achieved after transplant (10^9/L),
- The LDH value at diagnosis (U/L),
- Diagnosis of TA-TMA established as per laboratory/clinical markers indicating TMA.
 - o Presence of schistocytes in the peripheral blood smear (yes or no),
 - Absolute number of schistocytes per high power field in the peripheral blood smear (per hpf),
 - o Was any biopsy performed to confirm the histologic diagnosis of TA-TMA (yes or no),
 - If yes, sample location,
 - o De novo anemia at diagnosis (yes or no)
 - The most recent pre-transfusion hemoglobin (Hb) level at diagnosis (g/dL),
 - Proteinuria at diagnosis (yes or no),

Page 21 of 39

- The most recent rUPCR value at diagnosis (mg/mg).
- The most recent proteinuria value at diagnosis (mg/dL),
- Elevated plasma concentration of Sc5b-9 above ULN (yes or no),
 - Sc5b-9 level at diagnosis (ng/mL),
- Arterial hypertension defined by systolic blood pressure (BP) ≥ 140 mmHg and/or diastolic BP ≥ 90 mmHg (yes or no),
 - The pre-antihypertensive therapy systolic blood pressure (mmHg),
 - The pre-antihypertensive therapy diastolic blood pressure (mmHg),
 - Patients taking any antihypertension medication (yes or no),
 - Number of ongoing medications, excluding diuretics,
 - 0 medication,
 - ≤ 2 medications,
 - > 2 medications,
- o Time between HSCT and TA-TMA diagnosis (days),
- o Time between TA-TMA diagnosis and study enrollment (days).
- o TA-TMA persisting despite initial management of any triggering condition (yes or no),
- o Any sign/symptom of kidney dysfunction (yes or no),
 - The most recent serum creatinine value (mg/dL),
 - The last serum creatinine value pre-transplant (mg/dL),
 - Patients requiring renal replacement therapy (yes or no),
- Any sign/symptom of lungs dysfunction (yes or no),
 - The lowest oxygen level in the blood (%),
 - Patients receiving noninvasive positive pressure ventilation (yes or no),
 - Patients receiving invasive positive pressure ventilation (yes or no),
- Any sign/symptom of cardiovascular dysfunction (yes or no),
 - Patients with pulmonary hypertension diagnosis (yes or no),
 - If yes, the diagnostic method,
- Any sign/symptom of serositis (yes or no),
 - Patients with pleural effusion,
 - Patients with pericardial effusion,
 - Patients requiring pericardiocentesis,
 - Patients requiring thoracocentesis,
- Any sign/symptom of central nervous system (CNS) dysfunction (yes or no),
 - Patients with diagnosis of posterior reversible encephalopathy syndrome (PRES) (yes or no),
- o Any biopsy-proven GI involvement of TA-TMA (yes or no).

HSCT disease history data will be summarized. The following HSCT variables will be assessed:

- Underlying disease diagnosis,
- Donor type,
- Stem cell source,
- Transplant manipulation (yes or no),
- Type of conditioning regimen,
- Total-body irradiation (TBI) (yes or no),
- Time from start of conditioning regiment until TA-TMA diagnosis (days).
- Donor chimerism (%),
- Time from confirmed engraftment until TA-TMA diagnosis (days),
- Graft-versus-host disease (GVHD) prophylaxis (pre TA-TMA diagnosis) (yes or no),
- If yes, name of GVHD prophylaxis,
- GVHD Diagnosis (yes or no),
- Time from GVHD onset until TA-TMA diagnosis (days),

Protocol Sobi.PEGCET-201 Page 22 of 39

- GVHD grade according to the International Bone Marrow Transplant Registry Severity Index,
- Presence of infection (yes or no),
- · Presence of donor-specific antibodies (yes or no),
- Post-transplant treatments (yes or no),
- Post-transplant treatment type.

8.7.3 PRIOR AND CONCOMITANT MEDICATIONS AND PROCEDURES

Use of prior medications (stopped before treatment started) and concomitant medications (ongoing at treatment start or started after the first study treatment) will be coded using the latest World Health Organization-Drug Dictionary (WHO-DD) and tabulated on the Anatomical Therapeutic Chemical (ATC) 2, ATC 4, and PT levels.

Medications will be sorted in descending order of frequency of ATC 2 category based on the total. Patients may have more than 1 medication per ATC class and PT. At each level of summarization, a patient is counted once if he/she reported & or more medications at that level. Within each ATC 2 category, the ATC 4 category will be sorted in descending order of frequency based on the total. Within each ATC 4 category, PTs will be sorted in descending order of frequency based on the total. In case of identical frequencies, ATC2, ATC4, or PT will be sorted alphabetically.

Surgeries and other procedures will also be coded using MedDRA and summarized by SOC and PT. They will be classified as pre-treatment or on-treatment, similar to the medications described above.

8.7.4 EXPOSURE TO STUDY TREATMENT

Overall exposure to pegcetacoplan will be summarized using the following parameters:

- Total dose administered (mg) per patient throughout the study,
- Total time on study treatment (days) calculated as the time in days from the first study drug infusion date until the last study drug infusion date,
- Number and percentage of patients receiving treatment for exactly 12 weeks or exactly 16 weeks.
- Number and percentage of patients receiving infusions,
 - o Number and percentage of patients with all infusions completed (Infusion is considered complete if volume administered [at least equals] ≥ 80 % of volume prepared),
 - Number and percentage of patients with any infusions missed (i.e., planned infusion not done),
 - Number and percentage of patients with any infusions permanently interrupted,
 - Number and percentage of patients with any infusions interrupted and restarted,
 - Number and percentage of patients receiving exactly 1, exactly 2, etc. infusions.
- Number of started infusions,
- Number and percentage of started infusions completed (Infusion is considered complete if volume administered [at least equals] ≥ 80 % of volume prepared) based on all started infusions,
- Number and percentage of interrupted infusions based on all started infusions,
- Number and percentage of permanently interrupted infusions based on all started infusions,
- Number and percentage of interrupted and restarted infusions based on all started infusions.
- Number and percentage of patients having exactly 1, exactly 2, etc., interrupted infusions,
- Number and percentage of patients having exactly 1, exactly 2, etc., interrupted, and restarted infusions.
- Number and percentage of patients having exactly 1, exactly 2, etc. permanently interrupted infusions.

8.7.5 STUDY TREATMENT COMPLIANCE

All the details related to the IMP administration originate from the "Pegcetacoplan administration" eCRF form, regardless of the infusion site. The clinic and non-clinic administrations will be included in the calculation of compliance.

Two measures of compliance will be calculated in the study: infusion-level compliance and volume-level compliance.

Infusion-level compliance is defined as the total number of study infusions administered from the first infusion to the last infusion, multiplied by 100 and divided by the expected number of infusions. In case of premature treatment discontinuation, the expected number of infusions will be calculated for the period up to treatment discontinuation. The exact number of expected infusions will be calculated based on the total number of days from the date of the first study drug infusion till the date of treatment discontinuation. The rules are as follows:

- If time on treatment is less than 7 days, then expected number of infusions = floor ((time on treatment (days)+1)/2)
- If time on treatment is 7 days or more, then expected number of infusions = 3 + floor ((time on treatment (days) 5)/3)

Floor in the above derivations refers to rounding down to the closest integer.

Volume-level compliance will be defined as the total volume of study drug administered divided by the total volume that had to be administered (based on the total amount of infusions expected, calculated as described above).

Both compliance measures will be summarized as numeric values. In addition, the number and percentage of subjects who had treatment compliance in the three categories [80%; 90%], [90%; 100%] and [80%, 100%] will be presented.

8.8 PHARMACOKINETIC AND EFFICACY ENDPOINTS AND ANALYSES

Unless otherwise specified, all PK and efficacy analyses will be done on ITT set.

8.8.1 ANALYSIS OF PRIMARY ENDPOINTS

Individual serum pegcetacoplan concentrations, actual sampling times, and deviations from nominal sampling times will be presented in a data listing for all subjects included in the PK Set. Pegcetacoplan concentrations will be summarized with descriptive statistics at each scheduled time point (day and time post-dose). The number of subjects with a below limit of quantification (BLQ) value will also be tabulated. Concentrations that are BLQ will be treated as zero for the computation of descriptive statistics, except geometric mean. For the calculation of the geometric mean, they will be treated as equal to the LOQ. Missing values will be omitted from the calculation of descriptive statistics. Individual and median serum pegcetacoplan concentrations across time will be presented graphically on both linear and semi-logarithmic concentration scales. Actual sampling times will be used for the graphical presentation of individual concentration-time data, and nominal sampling times will be used for mean (SD) concentration-time plots.

Page 24 of 39

For linear concentration scale plots of individual concentration-time data, BLQ will be set to 0. For semi-logarithmic concentration scale plots, BLQ values will be set equal to the LOQ. If a BLQ value falls between two quantifiable concentrations, the value will be set equal to the LOQ, unless its exclusion can be justified (e.g., implausibility given the profile observed and known PK properties).

The PK analysis is performed by noncompartmental analysis using the WinNonlin software by Amador Biosciences, according to Amador's SOPs. PSI Biostats will only present the derived PK parameters as calculated by Amador Biosciences. For the estimation of PK parameters, concentrations that are recorded as BLQ prior to the first quantifiable value will be set to 0. Concentrations that are recorded at the end of the sampling period (i.e., no further quantifiable concentrations) will be set to missing and will not be used for the estimation of parameter values. If a BLQ value falls between two quantifiable concentrations, the value will be set to LLOQ/2, unless its exclusion can be justified, based on implausibility of the observed PK profile (e.g., if pivotal concentration values around C_{max} or several values are missing). In these cases when the AUC cannot be reliably determined, PK parameters will not be calculated. Furthermore, such cases will be described in the CSR.

Actual sampling time from start of infusion will be used for parameter estimation except for predose data points, which will be set to 0. If actual sampling time is missing, the planned time should be used. If a predose sample is taken after dosing, it will be taken as missing. AUC is calculated using the linear-log trapezoidal rule.

The following PK parameters will be calculated:

Day 1 (induction phase):

- AUC_{0-tau}: area under the concentration-time curve over the dosing interval, as calculated by the linear-log trapezoidal method.
- C_{max}: maximum observed serum concentration.
- T_{max}: time to the maximum observed serum concentration. If the maximum value occurs at more than 1 time point, T_{max} is defined as the first time point with this value.

Day 3 (induction phase):

- AUC_{0-tau}:
- C_{max}
- T_{max}: If the maximum value occurs at more than 1 time point, T_{max} is defined as the first time point with this value.

Day 5 (induction phase):

- AUC_{0-tau}:
- C_{max}
- T_{max}: If the maximum value occurs at more than 1 time point, T_{max} is defined as the first time point with this value.

Day 8 and onwards (s.c. maintenance phase):

C_{trough}: observed serum concentration predose.

Serum PK parameters C_{max}, AUC_{tau} and T_{max} and C_{trough} concentrations will be summarized including N,

Page 25 of 39

arithmetic mean, standard deviation, coefficient of variation, minimum, maximum, Q1, Q3, and median. In addition, geometric means and corresponding 95% confidence intervals will be calculated for AUC parameters, and C_{max} . For t_{max} , the geometric mean and its 95% CI, SD are not calculated. Figures: individual pegcetacoplan concentration-time curves and mean (SD) concentration-time profiles will be created to present the repeated-dose profile obtained from Day 1 to Day 8.

Additional PK analyses may be performed if deemed appropriate.

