5. SAMPLE SIZE AND POWER CALCULATION

This is a pilot study, and the sample size is based on practical rather than statistical aspects.

A total of 12 patients will be included and treated in the study. With 12 patients included, it is estimated that 9 patients will complete at least 4 weeks of treatment, which is deemed sufficient to characterize the PK of pegcetacoplan in patients with TA-TMA to an appropriate precision. In addition, 12 patients will provide a 72% probability to observe a response rate of at least 8 responders of the 12 patients recruited (assuming the true response rate is 70%).

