6. ANALYSIS ENDPOINTS

6.1 PRIMARY ENDPOINTS

The primary PK endpoints of this study are PK parameters for pegcetacoplan on Day 1, 3, and 5: Area under the concentration-time curve over the dosing interval on days 1 to 3 ($AUC_{0-taud1-d3}$), 3 to 5 ($AUC_{0-taud3-d5}$) and 5 to 8 ($AUC_{0-taud5-d8}$). Maximum observed serum concentration (C_{max}), Time to the maximum observed serum concentration (T_{max}) and Observed serum trough concentration pre-dose (T_{tough}) at all visits.

The primary safety endpoints are as follows:

- Occurrence of treatment-emergent adverse events (TEAEs)
- Changes from baseline in laboratory parameters and vital signs
- · Occurrence of clinically significant abnormal electrocardiogram (ECG) findings
- Presence of antibodies to polyethylene glycol (PEG) and pegcetacoplan throughout treatment and follow-up periods

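### The SAP's rule for an unreliable AUC withholds PK parameters without limit, so an evaluable Cmax and Tmax can be lost with it

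*SAP*

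**What the plan says.** SAP 6.1 names the AUC over each of the three induction intervals (Days 1 to 3, 3 to 5 and 5 to 8), Cmax, Tmax and Ctrough as the primary PK endpoints.

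SAP 8.8.1 gives the rules for values below the limit of quantification (BLQ) in the noncompartmental analysis. A BLQ value between two quantifiable concentrations is set to half the limit, unless the observed profile is implausible enough to justify excluding it. The examples given are: "e.g., if pivotal concentration values around C_{max} or several values are missing". The next two sentences read: "In these cases when the AUC cannot be reliably determined, PK parameters will not be calculated" and "Furthermore, such cases will be described in the CSR".

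The section then lists the parameters to be calculated for Days 1, 3 and 5: AUC0-tau, Cmax and Tmax, each under the label of PK parameter. It defines the peak as "C_{max}: maximum observed serum concentration". Geometric means with 95% confidence intervals are planned for the AUCs and for Cmax.

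Protocol 6.5.4.1 and 8.3.3.1 list the same parameters and contain no rule for withholding them.

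**The concern.** The rule ties the reporting of every PK parameter to the reliability of one of them. AUC over a 48 or 72 hour interval needs samples across the whole interval. Cmax and Tmax need only the samples around the peak. A profile can therefore fail for AUC and still give a sound Cmax and Tmax, and the sentence as written would withhold those too.

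The SAP does not say whether the withholding applies to the dosing day or to the patient. Neither document restores Cmax or Tmax elsewhere. With 12 patients, each evaluable value of a primary endpoint counts.

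**Working it through.** **The plan's own figure.** No figure in the plan bears on this rule. The only computable figure in SAP 5, the 72% probability of at least 8 responders of 12 at a true rate of 70%, reproduces (binomial tail 0.7237) and is unaffected.

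**Can AUC fail while Cmax holds?** Protocol 6.5.4 and Table 1 schedule samples on Days 1, 3 and 5 at predose, 15 min, 30 min, 1 h, 4 h, 8 h and 24 h. The rest of each interval rests on the next predose sample, and SAP 8.8.1 treats a predose sample taken after dosing as missing.

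- Interval lengths: Days 1 to 3 and 3 to 5 are 48 h each; Days 5 to 8 is 72 h.
- If the 24 h and next predose samples are both unusable, nothing is observed after 8 h. The unobserved share is (48 − 8)/48 = 83%, or (72 − 8)/72 = 89%.
- If the peak falls within the first 8 h (an assumption), Cmax and Tmax are still evaluable from the earlier samples.

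The same can happen when the trigger is confined to an excluded BLQ value. Suppose the 24 h value is BLQ between a quantifiable 8 h value and a quantifiable next predose value, and is excluded as implausible. The gap is then 40 h of 48 h, or 64 h of 72 h. AUC may be judged unreliable while the samples around the peak are intact.

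**Precision if Cmax is withheld.** On the log scale, the half-width of the 95% confidence interval for the geometric mean is t(0.975, n−1)/√n × SD of the logs. With the SD held fixed, only the multiplier changes:

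| n | multiplier | widening against n = 12 |
|---|---|---|
| 12 | 0.6354 | – |
| 11 | 0.6718 | 0.6718/0.6354 − 1 = 5.7% |
| 10 | 0.7154 | 0.7154/0.6354 − 1 = 12.6% |
| 9 | 0.7687 | 0.7687/0.6354 − 1 = 21.0% |

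**On the original scale.** The documents give no PK variability, so a geometric CV of 20% to 50% is assumed. The factor by which each limit lies from the geometric mean is exp(multiplier × √ln(1 + CV²)):

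| n | CV 20% | CV 30% | CV 50% |
|---|---|---|---|
| 12 | 1.13 | 1.21 | 1.35 |
| 10 | 1.15 | 1.23 | 1.40 |
| 9 | 1.16 | 1.25 | 1.44 |

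**The case against.** The strongest reply is that the trigger is narrow. The sentence follows one about an embedded BLQ value that is excluded for implausibility, and its opening words point back there. BLQ values at the end of a profile have their own rule, with no instruction to withhold anything. This stands in part. The examples in the parenthesis are about missing values, however, so an analyst could apply the rule more widely, and the 24 h example above shows that even the narrow reading can cost a valid Cmax.

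Second, one of the two named examples is missing values around the peak. Cmax and Tmax are then unreliable and withholding them is correct. This stands, and the fix preserves it.

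Third, the data are not thrown away. Individual concentrations are listed and plotted, concentrations are summarised at each scheduled time point, and affected cases go into the study report. Additional PK analyses are allowed, and Protocol 8.3.3.1 plans a separate population PK analysis. This limits the loss but does not return the value to the Cmax and Tmax summaries. Ctrough, taken predose from Day 8 onwards, does not depend on an AUC profile.

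Fourth, the noncompartmental analysis follows the PK vendor's procedures, which are not in the documents. They may already treat each parameter separately, but the SAP does not say so.

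A reader might also infer that the rule selects more stable patients into the Cmax summary, because those who deteriorate early have incomplete sampling. The documents give no rate of incomplete profiles on Days 1 to 5 and nothing linking incompleteness to outcome. The statement in SAP 5 that "it is estimated that 9 patients will complete at least 4 weeks of treatment" concerns four weeks of treatment, so it supports neither that inference nor an expected n of 9 for Cmax.

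**Conclusion.** The point holds as a wording defect with a modest effect. SAP 8.8.1, followed literally, can withhold evaluable values of two primary PK endpoints because a third could not be determined.

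The size depends on how many profiles are affected, which the documents do not allow anyone to estimate. Under an assumed loss of 1 to 3 of 12 profiles on a dosing day, the log-scale interval for geometric mean Cmax widens by about 6% to 21%. At an assumed CV of 30%, the loss of 3 moves the factor from 1.21 to 1.25.

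The analysis is descriptive, so no test, error rate or sample size figure changes. No claim of bias is made.

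**What to change.** Replace the sentence in SAP 8.8.1 with:

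> In these cases AUC0-tau for the affected dosing interval will not be calculated; Cmax and Tmax for that interval will still be reported when the samples around the peak are available.

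This sets the unit as the dosing interval, keeps the withholding where the peak itself is not observed, and works under either reading of the trigger. It needs no new data. Whether the samples around the peak are adequate remains a judgement, but the current text already calls for that judgement.

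The cost is one sentence. N may differ between AUC and Cmax or Tmax in the summary table; the SAP already plans to report N with these summaries.
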